[Appendix 5](#) of the protocol Amendment 5 for details. Given that uncertainty around this variability estimate remained, a second BVA using the same approach as specified in [Appendix 5](#) of the protocol Amendment 5 was performed to confirm the estimate after approximately 27 patients completed the Week 52 primary endpoint assessment. Based on this second blinded assessment, the sample size was set to 48 patients while maintaining the 2:1 allocation ratio. As there was no treatment comparison involved, no inflation of the type I error from this procedure was expected, and no adjustment to the significance levels for the final analysis was necessary.

Patients will be randomized (open-label, assessor-blinded) in a 2:1 allocation ratio between the idursulfase-IT treatment regimen and no IT treatment groups. Although this is a multi-center study, the randomization will not be stratified by center. The baseline GCA score (at Screening Visit) is expected to be a key prognostic factor. Therefore, the randomization will be stratified according to baseline GCA score: ≤ 70 versus > 70 . The randomization schedule will be generated and administered centrally by Pharmaceutical Product Development, LLC (PPD), independent of the sponsor's project team. There is no replacement of patients who do not complete the study.

In a separate substudy, additional patients with cognitive impairment may be enrolled who are below the age of 3 years at the time of informed consent. All patients meeting eligibility criteria for the substudy will be enrolled until enrollment for the pivotal study is completed. There is no target sample size. Such patients are ineligible for the pivotal trial and will not be randomized, but will receive idursulfase-IT treatment monthly.

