6.7.1 Primary Analysis

For the pivotal study, the primary efficacy endpoint is the change from study baseline (Screening Visit) to Visit Week 52 in the General Conceptual Ability (GCA) score as measured by the DAS-II. The primary analysis will compare the treatment groups using a linear mixed model repeated measures (MMRM) analysis (Malinckrodt et al. 2008; Siddiqui et al. 2009). The repeated measures are the change from baseline GCA score obtained at the scheduled Visit Weeks 16, 28, 40, and 52, respectively. The model will include fixed categorical effects for treatment, visit week, treatment by visit week interaction, baseline GCA classification factor (either ≤ 70 or > 70), baseline age group (either < 6 years or ≥ 6 years), treatment by baseline GCA classification factor interaction, treatment by baseline age group interaction, interaction between baseline GCA classification factor and baseline age group, genotype, and the baseline GCA score as a continuous covariate. Visit week is defined as nominal visits, unless specified otherwise.

SAS Proc Mixed with restricted maximum likelihood estimation (REML) and an unstructured within-patient covariance structure will be used. If this model fails to converge, a first order autoregressive (AR(1)) covariance structure will be used for the primary analysis. Due to small sample size of ITT Population with baseline age ≥ 6 years, MMRM model may fail to converge when low count of subjects with baseline age ≥ 6 years exists in either treatment group. If this model fails to converge, the treatment by baseline age group interaction and /or interaction between baseline GCA classification factor and baseline age group will be removed from the model. The Kenward-Roger approximation will be used to estimate denominator degrees of freedom for tests of fixed effects. The assumptions of the model, including normality, will be evaluated using residual and other diagnostic plots of model fit.

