6.7.4 Subgroup Analyses

Subgroup analyses will be performed for the following subgroups:

- Baseline GCA classification groups. For this analysis, patients with a baseline GCA score of > 70 will be classified as having “Moderate” cognitive impairment, while patients with a baseline GCA score ≤ 70 will be classified as having “Severe” cognitive impairment. The randomization is stratified by this classification variable to ensure treatment group balance within these subgroups
- Baseline age group (either < 6 years or ≥ 6 years)
- Exploratory analysis for baseline age group (either < 55 months or ≥ 55 months).

Subgroup analyses are planned for the change from baseline in GCA and ABC standard scores, respectively. An MMRM model will be used to test for treatment by subgroup interactions. Interactions with a significance level of less than 10% will be considered potentially important and flagged for further clinical assessment. In general, the model will include fixed categorical effects for treatment, visit week, treatment by visit week interaction, subgroup, treatment by subgroup interaction, subgroup by visit interaction and the 3-way interaction between treatment, visit week and subgroup, and genotype. The p-values of interaction terms will be presented, as well as the least squares means and its 95% confidence intervals by treatment and visit for each subgroup classification factor. Descriptive statistics of the observed and change from baseline GCA and ABC standard scores will also be presented by treatment and visit week within each subgroup.

Additionally, the subgroup analysis will be performed for the age subgroup with baseline age < 6 years which may be the patient population with the most potential to benefit from the idursulfase-IT treatment. The change from baseline GCA score obtained at Visit Week 52 will be compared between the treatment groups using MMRM analysis. The repeated measures are the change from baseline GCA score obtained at the scheduled Visit Weeks 16, 28, 40, and 52, respectively. The model will include fixed categorical effects for treatment, visit week, treatment by visit week interaction, baseline GCA classification factor (either ≤ 70 or > 70), treatment by baseline GCA classification factor interaction, genotype and the baseline GCA score as a continuous covariate. Due to small sample size of ITT subjects with baseline age ≥ 6 years, MMRM model will not be applied for this age subgroup.

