The sample SAS code is presented in [appendix 9.2.9](#).

As exploratory analysis, the subgroup analysis will also be performed for the age subgroup with baseline age < 55 months and ≥ 55 months using an MMRM analysis in the same manner as described above for age subgroup with baseline age < 6 years.

The subgroup analyses will also be performed for the baseline GCA subgroup with baseline GCA score ≤ 70 and baseline GCA score > 70 . The change from baseline GCA score obtained at Visit Week 52 will be compared between the treatment groups using MMRM analysis. The repeated measures are the change from baseline GCA score obtained at the scheduled Visit Weeks 16, 28, 40, and 52, respectively. The model will include fixed categorical effects for treatment, visit week, treatment by visit week interaction, baseline age group (either <6 years or ≥ 6 years), treatment by baseline age group interaction, genotype and the baseline GCA score as a continuous covariate.

The sample SAS code is presented in [appendix 9.2.10](#).

The estimated least squares means and 95% confidence intervals on the treatment comparison at Visit Weeks 16, 28, 40, and 52 from MMRM model will be presented in Forest plots, including subgroup of baseline age < 6 years, baseline age < 55 months and baseline age ≥ 55 months, baseline GCA score ≤ 70 and baseline GCA score > 70 .

As exploratory analyses, the primary and key secondary MMRM models will be refit including the continuous baseline covariate by treatment interaction term and the 3-way interaction among treatment, visit week and the continuous baseline covariate in the model. The p value for the interaction terms and the estimated least squares means with their standard errors and 95% confidence intervals by treatment and visit at quartiles of GCA at baseline (25th, 50th and 75th percentiles) will be presented.

Due to small sample size of ITT Population with baseline age ≥ 6 years, MMRM model may fail to converge when low count of subjects with baseline age ≥ 6 years exists in either treatment group. If this model fails to converge, the treatment by baseline age group interaction will be removed from the model.

The sample SAS code is presented in [appendix 9.2.11](#).

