9.2.11 Sample SAS code for subgroup analysis testing treatment interaction

```
ods output estimates=est Tests3=FixF;  
ods graphics on;  
proc mixed data=adefc covtest;  
  class Trt VisitWk GCAclass Agegroup Genotype usubjid;  
  model GCAchgBL = Trt VisitWk GCABL Trt*Visitwk Trt* GCABL Trt*Visitwk*GCABL  
  GCAclass Agegroup Genotype/ ddfm=kr solution;  
  repeated VisitWk / type=un subject=usubjid rcorr;  
  estimate "Trt diff at Week 16" GCABL 25th_of_BL_GCA_distribution Trt 1 -1 Trt*VisitWk  
  1 0 0 0 -1 0 0 0 / cl;  
  estimate "Trt diff at Week 28" GCABL 25th_of_BL_GCA_distribution Trt 1 -1 Trt*VisitWk  
  0 1 0 0 0 -1 0 0 / cl;  
  estimate "Trt diff at Week 40" GCABL 25th_of_BL_GCA_distribution Trt 1 -1 Trt*VisitWk  
  0 0 1 0 0 0 -1 0 / cl;  
  estimate "Trt diff at Week 52" GCABL 25th_of_BL_GCA_distribution Trt 1 -1 Trt*VisitWk  
  0 0 0 1 0 0 0 -1 / cl;  
  estimate "Trt diff at Week 16" GCABL 50th_of_BL_GCA_distribution Trt 1 -1 Trt*VisitWk  
  1 0 0 0 -1 0 0 0 / cl;  
  estimate "Trt diff at Week 28" GCABL 50th_of_BL_GCA_distribution Trt 1 -1 Trt*VisitWk  
  0 1 0 0 0 -1 0 0 / cl;  
  estimate "Trt diff at Week 40" GCABL 50th_of_BL_GCA_distribution Trt 1 -1 Trt*VisitWk  
  0 0 1 0 0 0 -1 0 / cl;  
  estimate "Trt diff at Week 52" GCABL 50th_of_BL_GCA_distribution Trt 1 -1 Trt*VisitWk  
  0 0 0 1 0 0 0 -1 / cl;  
  estimate "Trt diff at Week 16" GCABL 75th_of_BL_GCA_distribution Trt 1 -1 Trt*VisitWk  
  1 0 0 0 -1 0 0 0 / cl;  
  estimate "Trt diff at Week 28" GCABL 75th_of_BL_GCA_distribution Trt 1 -1 Trt*VisitWk  
  0 1 0 0 0 -1 0 0 / cl;  
  estimate "Trt diff at Week 40" GCABL 75th_of_BL_GCA_distribution Trt 1 -1 Trt*VisitWk  
  0 0 1 0 0 0 -1 0 / cl;  
  estimate "Trt diff at Week 52" GCABL 75th_of_BL_GCA_distribution Trt 1 -1 Trt*VisitWk  
  0 0 0 1 0 0 0 -1 / cl;  
  lsmeans "Trt lsmeans at Q1" trt01pn*avisitn / at blgcass=Q1 / cl;  
  lsmeans "Trt lsmeans at Q2" trt01pn*avisitn / at blgcass=Q2 / cl;  
  lsmeans "Trt lsmeans at Q3" trt01pn*avisitn / at blgcass=Q3 / cl;  
run;  
Repeat for change from baseline in ABC score
```

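### The exploratory refit includes treatment × visit × baseline without baseline × visit, so half of the three-way test's 6 df measure a baseline effect common to both arms

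*SAP*

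**What the plan says.** The last exploratory analysis in SAP 6.7.4 refits the primary and key secondary models with two additions: the continuous baseline score by treatment, and "the 3-way interaction among treatment, visit week and the continuous baseline covariate in the model". Of the results, "The p value for the interaction terms and the estimated least squares means with their standard errors" and 95% confidence intervals are to be presented, by treatment and visit, at the baseline quartiles.

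The models being refit bring no baseline-by-visit term with them. In SAP 6.7.1 the last items of the model are "genotype, and the baseline GCA score as a continuous covariate", so the score enters as a main effect only. SAP 6.7.2 treats baseline ABC in the same way. The code in SAP 9.2.11 agrees with the text: it begins "model GCAchgBL = Trt VisitWk GCABL Trt*Visitwk Trt* GCABL Trt*Visitwk*GCABL" and continues with GCAclass, Agegroup and Genotype. VisitWk*GCABL does not appear.

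The categorical subgroup model in the same section is built differently. It carries "subgroup by visit interaction and the 3-way interaction between treatment, visit week and subgroup, and genotype", so there the lower-order term is present. Protocol 10.5.4 planned only the baseline-by-treatment term for the continuous refit; the three-way term was added in the SAP.

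**The concern.** When a three-way term is fitted without one of its two-way components, it absorbs that component. Here the term labelled treatment × visit × baseline also carries any change over time in the baseline slope that is the same in both arms. Such a change says nothing about whether benefit depends on baseline score, yet it can make the three-way p-value small.

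The trigger is plausible for GCA. The outcome is change from baseline in a disease that SAP Appendix III models as a steady decline, and SAP 4.2 states: "The baseline GCA score (at Screening Visit) is expected to be a key prognostic factor". If baseline score predicts the rate of decline, its effect on change grows from visit to visit. No section assumes that the baseline effect is constant over visits. A reader who sees a small three-way p-value would naturally conclude that the treatment effect varies with baseline cognition, a question that SAP 6.7.4 is there to explore.

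**Working it through.** **Plan's own figure.** The documents give no operating characteristic for this test, so only the shared design inputs can be reproduced. SAP 4.2 gives 80% power for 11 points, SD 11.6, 32:16 and up to 10% missing. With 29:14 evaluable, the noncentrality is 11 / (11.6 × √(1/29 + 1/14)) = 2.91 on 41 df, and power is 81.2%. With 28:14 it is 80.7%. The stated 80% is reproduced.

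**Degrees of freedom.** Let β(g,v) be the slope of change on baseline in arm g at visit v. There are 2 × 4 = 8 slopes.

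- As written, the model without the three-way term allows one slope per arm, so the test has 8 − 2 = 6 df. Its null hypothesis is that, within each arm, the slope is the same at all four visits.
- With VisitWk*baseline included, the model without the three-way term has 1 + 1 + 3 = 5 slope parameters, so the test has 8 − 5 = 3 df. Its null hypothesis is that the difference in slope between the arms is the same at all visits.

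If β(g,v) depends on v but not on g, the first null is false and the second is true. The column rank of the SAP 9.2.11 design (48 patients, 4 visits, five genotype categories as in SAP 6.5) confirms the count:

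| Model | Rank |
|---|---|
| Without the three-way term | 16 |
| Adding Trt*VisitWk*GCABL (as written) | 22 |
| Adding VisitWk*GCABL only | 19 |
| Adding both | 22 |

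The as-written test has 22 − 16 = 6 df, and the corrected test has 22 − 19 = 3 df. The full model has rank 22 either way, so its fitted values are identical.

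**False-positive rate.** Inputs from SAP Appendix III: baseline normal(70, 15) restricted to 55–85, and AR(1) covariance with ρ = 0.80 and SDs 3, 5, 8 and 10 at Months 4, 7, 10 and 13. From SAP 4.2: 32:16 patients. Assumed: a slope equal in both arms and growing linearly, b × m/13 at month m, so that b is the Week 52 slope. For b = 0.5 the four slopes are 0.15, 0.27, 0.38 and 0.50. The true three-way effect is zero. Data are complete, and the class covariates are left out. There were 4,000 trials per setting, with exact F tests (Wilks for 6 df, Hotelling for 3 df). At a true 10% the simulation error is √(0.1 × 0.9 / 4,000) = 0.5 percentage points.

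| b | As written, 5% level | As written, 10% level | With VisitWk*GCABL, 10% level | As written, 10% level, SDs × 1.16 |
|---|---|---|---|---|
| 0 | 4.7% | 9.7% | 9.4% | 10.3% |
| 0.2 | 8.4% | 15.6% | 10.4% | 13.2% |
| 0.3 | 15.4% | 24.6% | 10.3% | 19.2% |
| 0.5 | 35.2% | 48.7% | 10.2% | 38.1% |
| 0.7 | 63.1% | 74.6% | 9.2% | 62.8% |

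The last column scales the SDs so that Week 52 has the planning value of 11.6. A separate simulation with the unscaled SDs gave 15%, 23%, 48% and 76% for b = 0.2, 0.3, 0.5 and 0.7. With 43 patients (29:14) and SD 11.6, the 10%-level rates are 19.0% at b = 0.3 and 35.0% at b = 0.5.

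To put b on a familiar scale, the truncated baseline has SD 8.1, so the correlation with Week 52 change is 8.1b / √((8.1b)² + 10²). This is 0.16, 0.24, 0.38 and 0.49 for b = 0.2, 0.3, 0.5 and 0.7.

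The treatment-by-baseline test, averaged over visits, kept its level in every setting, at about 5% and 10%.

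**The case against.** The strongest reply is that this is one descriptive p-value in an exploratory analysis. SAP 8.5 leaves tests outside its three families unadjusted and has their p-values read descriptively; no decision depends on this one. The fitted means by arm and visit let a reader see whether the baseline slopes run in parallel. For GCA, the categorical model in the same section tests a related question with the lower-order term present. The size of the effect also rests on a slope that the documents do not give. All of this stands, and it limits the consequence. It does not make the p-value correct.

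Three stronger readings are tempting but unsupported.

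- A reader might infer that the test signals effect modification whenever baseline predicts decline. It does not. At b = 0.1 the 10%-level rate is 11.1%, and if the baseline effect is constant over visits the test is nominal.
- A reader might attach the rule "Interactions with a significance level of less than 10% will be considered potentially important and flagged for further clinical assessment" to this refit. That sentence belongs to the categorical subgroup models; the refit paragraph sets no threshold. The 10% level is used here as a yardstick, and the inflation is also present at 5%.
- A reader might conclude that the whole refit misleads. The treatment-by-baseline test and the quartile means are unaffected by the omission.

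**Conclusion.** The omission is present in both text and code, and the three-way p-value as specified does not test what its label says. Under the SAP's own simulation covariance with 48 complete patients, its 10%-level false-positive rate goes from nominal with no common baseline-by-time effect to about 15%, 23–25%, 48% and 75% at assumed Week 52 slopes of 0.2, 0.3, 0.5 and 0.7. With the planning SD of 11.6 it is lower but still inflated. The slope range and its linear growth are assumptions. The sizes apply to GCA; for ABC the algebra is the same, but the documents do not say that baseline ABC is prognostic. The primary and key secondary conclusions are not touched. The point deserves correction because the p-value is to be presented.

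**What to change.** Add VisitWk*GCABL to the refit in SAP 6.7.4 and to the model statement in SAP 9.2.11, and VisitWk*ABCBL to the ABC version. The three-way term then has 3 df and tests only whether the arm difference in baseline slope changes over visits. This matches the structure of the categorical subgroup model in the same section. In all settings run, the corrected test stayed at 4.3–5.9% for a 5% level and 8.7–11.5% for a 10% level, simulation error included. The cost is one term in the text and one in the code. Because the rank stays at 22, no model degrees of freedom are spent and the fitted means do not change.

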10.5.4 Exploratory Analyses

As exploratory analyses, the primary and key secondary MMRM models will be refit including the continuous baseline covariate by treatment interaction term in the model. Estimated least square means and 95% CIs for each treatment adjusting at the 25th, 50th, and 75th percentiles of the pooled baseline covariate distribution will be evaluated.

Additional subgroup analyses are planned for exploratory purposes for the change from baseline in GCA and ABC scores. An MMRM model will be used to test for subgroup interactions at the 10% significance level. In general, the model will include effects for treatment, visit week, treatment by visit week interaction, subgroup, treatment by subgroup interaction, subgroup by visit interaction and the 3-way interaction between treatment, visit and subgroup. The p-values from interaction tests will be presented, as well as the least square means and 95% CIs by treatment and visit within each subgroup. Descriptive statistics of observed values and change from baseline will also be presented by treatment and visit week within each subgroup.

A subgroup analysis will be performed for baseline GCA groups. For this analysis, patients with a baseline GCA score of greater than 70 will be classified as having “Moderate” cognitive impairment, while patients with a baseline GCA score equal to or below 70 will be classified as having “Severe” cognitive impairment. The randomization is stratified by this classification variable to ensure treatment group balance within these subgroups. Similar exploratory subgroup analyses may be performed for age group (either ≤ 6 years or > 6 years), language, geographic region or other baseline factors using MMRM.

A linear random coefficients model (ie, random slope and intercept for continuous time) will be fit for the primary and key secondary endpoints if appropriate. The average of the subject-specific slope estimates from the model will be compared between treatment groups using the two-sample t-test. To explore the relationship between composite scores and their components, correlations between the GCA and ABC scores (absolute value and change from baseline) and their respective domain scores will be estimated. Scatter plots will also be presented.

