6.7.2 Key Secondary Analysis

The key secondary efficacy endpoint is the change from study baseline (Screening Visit) to Visit Week 52 in the Adaptive Behavior Composite (ABC) score as measured by the VABS-II. The key secondary analysis will compare the treatment groups using a linear mixed model repeated measures (MMRM) analysis. The repeated measures are the change from baseline ABC scores obtained at the scheduled Visit Weeks 16, 28, 40, and 52, respectively. The model will include fixed categorical effects for treatment, visit week, treatment by visit week interaction, baseline GCA classification factor (either ≤ 70 or >70), baseline age group (either <6 years or ≥ 6 years),

treatment by baseline GCA classification factor interaction, treatment by baseline age group interaction, interaction between baseline GCA classification factor and baseline age group, genotype, and the baseline ABC score as a continuous covariate.

SAS Proc Mixed with restricted maximum likelihood estimation (REML) and an unstructured within-patient covariance structure will be used. If this model fails to converge, a first order autoregressive (AR(1)) covariance structure will be used instead. The Kenward-Roger approximation will be used to estimate denominator degrees of freedom for tests of fixed effects. The assumptions of the model, including normality, will be evaluated using residual and other diagnostic plots of model fit.

From this model, least squares means, standard errors, treatment differences in least squares means, and 95% confidence intervals will be estimated for each time point. The significance test will be based on the treatment comparison of least squares means at Visit Week 52 from this model, and a p-value will be presented for this time point only. Estimated least squares means for change from baseline and the observed absolute values (\pm SE) by treatment group will be plotted over time.

The sample SAS code is presented in [appendix 9.2.2](#).

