8. STATISTICAL/ANALYTIC ISSUES

8.1 Adjustment for Covariates

Analyses of the change from baseline in efficacy endpoints utilizing MMRM methodology will adjust for the baseline score of the parameter of interest as a continuous covariate in the model. As the randomization of the study is stratified by the baseline GCA classification factor (either ≤ 70 or > 70), MMRM analyses will also take into account the GCA strata as a classification factor. The baseline age group (either < 6 years or ≥ 6 years) is also a categorical covariate in the MMRM analysis.

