9.2.2 Sample SAS code for the key secondary analysis

```
ods output estimates=est Tests3=FixF;
ods graphics on;
proc mixed data=adef data=adef covtest;
  class Trt VisitWk GCAclass Agegroup Genotype usubjid;
  model ABCchgBL = GCAclass Trt VisitWk Trt*Visitwk ABCBL Agegroup Trt*GCAclass
  Trt*Agegroup GCAclass* Agegroup Genotype / ddfm=KR residual;
  repeated VisitWk / type=un subject=usubjid rcorr;
  estimate "Trt diff at Week 16" Trt 1 -1 Trt*VisitWk 1 0 0 0 -1 0 0 0 / cl;
  estimate "Trt diff at Week 28" Trt 1 -1 Trt*VisitWk 0 1 0 0 0 -1 0 0 / cl;
  estimate "Trt diff at Week 40" Trt 1 -1 Trt*VisitWk 0 0 1 0 0 0 -1 0 / cl;
  estimate "Trt diff at Week 52" Trt 1 -1 Trt*VisitWk 0 0 0 1 0 0 0 -1 / cl;
  lsmeans Trt*VisitWk / cl;
run;
```

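### SAP 6.7.4 sets the evaluation points for the ABC baseline-by-treatment refit at quartiles of baseline GCA, although that model's continuous covariate is baseline ABC

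*SAP*

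**What the plan says.** SAP 6.7.4 (Subgroup Analyses) states that "the primary and key secondary MMRM models will be refit including the continuous baseline covariate by treatment interaction term", together with a three-way term with visit week. The next sentence gives one set of evaluation points for both refits: least squares means by treatment and visit "at quartiles of GCA at baseline (25th, 50th and 75th percentiles").

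The key secondary model is defined in SAP 6.7.2 with "genotype, and the baseline ABC score as a continuous covariate". The code in SAP 9.2.2 agrees: "model ABCchgBL = GCAclass Trt VisitWk Trt*Visitwk ABCBL Agegroup Trt*GCAclass". SAP 8.1 gives the general rule that the repeated-measures analyses "will adjust for the baseline score of the parameter of interest as a continuous covariate in the model".

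Protocol 10.5.4 plans the same exploratory refit for both endpoints, but evaluates it at the "25th, 50th, and 75th percentiles of the pooled baseline covariate distribution will be evaluated".

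SAP 9.2.11 has code for the GCA refit only, with baseline GCA and its percentiles throughout, and closes with "Repeat for change from baseline in ABC score".

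**The concern.** The refit is meant to show whether the treatment effect on adaptive behaviour depends on the boy's starting level of adaptive behaviour. A table at the lower quartile, median and upper quartile of baseline ABC answers that. The ABC model has no continuous GCA term, so a GCA quartile is either undefined in it or is entered as though it were an ABC score. In the second case the three columns carry quartile labels that do not belong to the ABC distribution, and a reader would attach the estimates to the wrong part of the trial population.

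Nothing in the plan makes the two distributions coincide. The inclusion criteria (Protocol 5.2.1) restrict GCA, mostly to 55–85, and set no range for ABC.

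**Working it through.** **Specification check.** The plan states no figure for this analysis, so there is none to reproduce. The relevant places, side by side:

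| Place | Continuous covariate for ABC | Evaluation points for ABC |
|---|---|---|
| Protocol 10.5.4 | the model's baseline covariate | percentiles of that covariate |
| SAP 6.7.2, 8.1, 9.2.2 | baseline ABC (ABCBL) | not stated |
| SAP 6.7.4 | the model's continuous baseline covariate | quartiles of baseline GCA |
| SAP 9.2.11 | GCA code only, then repeat for ABC | GCA percentiles in the code; none named for ABC |
| SAP 7.2 (changes from protocol) | – | no change listed |

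An analyst can proceed in three ways:

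1. Fit ABCBL and enter GCA quartiles as its values. This follows 6.7.4 literally, but the quartile labels are wrong.
2. Keep baseline GCA (GCABL) as the continuous covariate in an ABC model. The GCA quartiles then fit, but it is no longer the key secondary model of 6.7.2, 8.1 and 9.2.2.
3. Fit ABCBL at ABC quartiles. This agrees with Protocol 10.5.4 but departs from the words of 6.7.4.

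**Consequence of route 1.** At a given visit, write the treatment difference at baseline ABC value b as d + g·b, where g is the interaction slope and d collects the terms that do not involve b. Evaluating at a GCA quartile instead of the ABC quartile changes the reported difference by

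shift = g × (Q_GCA − Q_ABC).

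**Illustration only.** SAP 9.3.2 simulates baseline GCA as normal, mean 70, SD 15, restricted to 55–85. Its quartiles are 70 + 15·Φ⁻¹(Φ(−1) + p[Φ(1) − Φ(−1)]), giving 63.4 / 70.0 / 76.6 for p = 0.25, 0.50, 0.75. The baseline ABC distribution and g are not in the documents, so the following are assumptions.

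- Take ABC as normal, mean 80, SD 12. Its quartiles are 80 ± 0.6745 × 12 and the mean: 71.9 / 80.0 / 88.1. The gaps are −8.5 / −10.0 / −11.5, and the GCA quartiles fall at the 8th, 20th and 39th ABC percentiles.
- Take g = 0.3 and a difference of 10 at the ABC mean.
  - At ABC quartiles: 10 + 0.3 × (71.9 − 80) = 7.6, then 10.0, then 10 + 0.3 × (88.1 − 80) = 12.4.
  - At GCA quartiles: 10 + 0.3 × (63.4 − 80) = 5.0, 10 + 0.3 × (70 − 80) = 7.0, 10 + 0.3 × (76.6 − 80) = 9.0.
  - A large simulated data set agreed to within 0.1.

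Changing the assumed ABC distribution (SD 8 to 12 throughout) moves the gap widely:

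| Assumed ABC mean | Gap, GCA quartile − ABC quartile |
|---|---|
| 65 | +3.5 to +6.5 |
| 70 | −1.5 to +1.5 |
| 75 | −6.5 to −3.5 |
| 80 | −11.5 to −8.5 |
| 85 | −16.5 to −13.5 |

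The shift can therefore have either sign. It is close to zero if the two distributions are centred alike, and exactly zero if g = 0.

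**The case against.** The strongest reply is that the rest of the plan points to the right execution. The interaction in 6.7.4 is defined by the model's own continuous baseline covariate, 8.1 fixes what that is, and the protocol refers to "percentiles of the pooled baseline covariate distribution". SAP 9.2 warns that dataset and variable names may differ. The paired code in 9.2.1 and 9.2.2 shows how the authors adapt a GCA template: the model statements differ only in the outcome and its baseline. An experienced programmer would probably use ABCBL at ABC quartiles. It is also possible that baseline GCA was meant as the modifier for both outcomes, since SAP 4.2 expects it to be a key prognostic factor. The GCA quartiles would then be correct, and the fault would lie in the description of the model.

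The first argument stands in part. A reader might infer that the reported ABC effects will be wrong. The documents do not support that, because route 1 is only one of three possible executions. It remains true that the sentence in 6.7.4 contradicts the model it governs, and that correct execution requires departing from it. The second argument conflicts with 6.7.2 and 8.1, so it too ends in a need to amend.

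A reader might also attach a size, for example a slope of 0.2–0.5 and a gap of 5–15 points giving 0.2 × 5 = 1.0 to 0.5 × 15 = 7.5 points, and set that against the 10-point ABC difference used for sizing. Both inputs would be assumptions, and the range leaves out the small, zero and opposite-sign cases shown above. The comparison also misleads, because the 10 points belong to the key secondary test, which uses a different model.

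Finally, an estimate at a given ABC value is valid for that value; only its quartile label would be wrong. Extrapolation beyond the ABC data cannot be established either. In the illustration the points lie inside the distribution, although with an assumed mean of 85 and SD of 8 the lowest would fall below the 1st percentile, Φ((63.4 − 85)/8) ≈ 0.003.

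**Conclusion.** The point holds as a specification error: SAP 6.7.4 prescribes evaluation points that do not fit the key secondary model, contradicts SAP 6.7.2, 8.1 and 9.2.2, and departs from Protocol 10.5.4 without being listed in SAP 7.2. Mislabelled ABC estimates follow only if the text is applied literally with ABCBL in the model. The shift is then g × (Q_GCA − Q_ABC), of unknown sign and size.

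The importance is low. The analysis is labelled exploratory and lies outside the three gatekeeping families of SAP 8.5. The key secondary test is unaffected. The interaction p-values are also unaffected as long as ABCBL is the covariate, because they do not depend on where the means are evaluated. What is at stake is the labelling and reproducibility of one exploratory table.

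**What to change.** In SAP 6.7.4, replace the reference to GCA quartiles with: *at the 25th, 50th and 75th percentiles of the pooled baseline score used as the continuous covariate in that model (GCA for the GCA model, ABC for the ABC model)*. In SAP 9.2.11, state that the ABC repeat uses ABCBL and baseline ABC percentiles.

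This restores Protocol 10.5.4, so no entry in SAP 7.2 is needed for it. The cost is one sentence and the matching code values, with no new data and no change to alpha. If baseline GCA really was intended as the modifier of the ABC effect, that should instead be written as a separate exploratory model and declared in 7.2.

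The coefficients in the ESTIMATE lines of 9.2.11 are a separate matter; correcting them would not settle this point.
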